Educational re-enrolment will be assessed for children who are not currently in school by asking parents whether or not they would want them to go back to school (0=No, 1=Yes).

[Time Frame: Baseline, 8-months post-baseline, and 12-months post-baseline]

Educational re-enrolment – Child Report

Educational re-enrolment will be assessed for children who are not currently in school by asking children whether or not they would want to go back to school (0=No, 1=Yes).

[Time Frame: Baseline, 8-months post-baseline, and 12-months post-baseline]

Parent support of education – Parent Report

Parental support for school will be measured by asking how often the parent engages in behaviours that support learning using a 5-point Likert scale (5 items, e.g., “I let my child’s schoolwork come first, before chores and responsibilities”). Higher scores reflect more parental support and value for school.

[Time Frame: Baseline, 8-months post-baseline, and 12-months post-baseline]

Parent support of education – Child Report

Parental support for school will be measured by asking how often the child’s male and female parent figures engage in behaviours that support learning using a 5-point Likert scale (10 items, e.g., “Your

male/female parent figure lets your schoolwork come first, before chores and responsibilities”). Higher scores reflect more parental support and value for school.

[Time Frame: Baseline, 8-months post-baseline, and 12-months post-baseline]

Child behaviour problems: Child and Adolescent Behaviour Inventory – Adult Report

Child behaviour problems will be measured using the Child and Adolescent Behaviour Inventory (CABI) [31]. The CABI assesses a wide range of internalising and externalising symptoms in children and adolescents and is relatively shorter than the Child Behaviour Check List (CBCL), making it a practical and reliable tool for measuring behaviour problems. Parents report on their child’s behaviour during the past month (0 = Not True, 1 = Somewhat or Sometimes True, 1 = Very True). The irritability subscale (4 items, e.g., “has frequent mood changes”) and the externalizing subscale (10 items, e.g., often lies or cheats) will be used to measure problem behaviours. The 14 items are summed to create a total score of child behaviour problems.

[Time Frame: Baseline, 8-months post-baseline, and 12-months post-baseline]

Child behaviour problems: Child and Adolescent Behaviour Inventory – Child Report

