Child behaviour problems will be measured using the Child and Adolescent Behaviour Inventory (CABI) [31]. The CABI assesses a wide range of internalising and externalising symptoms in children and adolescents and is relatively shorter than the Child Behaviour Check List (CBCL), making it a practical and reliable tool for measuring behaviour problems. Parents report on their child’s behaviour during the past month (0 = Not True, 1 = Somewhat or Sometimes True, 1 = Very True). The irritability subscale (4 items, e.g., “has frequent mood changes”) and the externalizing subscale (10 items, e.g., often lies or cheats) will be used to measure problem behaviours. Items are summed to create a total score of child behaviour problems.

[Time Frame: Baseline, 8-months post-baseline, and 12-months post-baseline]

Child substance use – Child Report

Child substance use will be measured using two items based on lifetime alcohol and tobacco consumption (e.g., “Have often do you drink alcohol?”). Responses will be based on a 4-point Likert scale of 0 to 3 (0=Never; 3=Often). Items will be summed with higher scores indicating more frequent substance use.

[Time Frame: Baseline, 8-months post-baseline, and 12-months post-baseline]

Child prosocial behaviour – Adult Report

Child prosocial behaviour will be assessed from items derived from the pre-post study of PfR (5 items; e.g., “Your child is considerate of other people’s feelings.”). Items are summed to create a total score of prosocial behaviour.

[Time Frame: Baseline, 8-months post-baseline, and 12-months post-baseline]

Child prosocial behaviour – Child Report

Child prosocial behaviour will be assessed from items derived from the pre-post study of PfR (5 items; e.g., “You are considerate of other people’s feelings.”). Items are summed to create a total score of prosocial behaviour.

[Time Frame: Baseline, 8-months post-baseline, and 12-months post-baseline]

Child respectful behaviour – Parent Report

Respectful behaviour by children will be assessed by asking parents one question about how often they see their children behaving well. Responses will be based on a 4-point Likert scale of 0 to 3 (0=Never; 3=Often). Items will be summed with higher scores indicating more frequent respectful behaviour.

[Time Frame: Baseline, 8-months post-baseline, and 12-months post-baseline]

Gender socialisation – Parent Report

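### Both CABI entries give two of the three answers the same code, and the Child Report entry names parents as respondents: a minor correction to a secondary outcome

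*Protocol*

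**What the plan says.** Protocol section 15, Secondary outcomes, has two CABI entries.

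- **Adult Report.** Parents rate the past month on three labelled answers. *Not True* is coded 0, and the other two are coded "1 = Somewhat or Sometimes True, 1 = Very True". Four irritability items and ten externalising items are used, and "The 14 items are summed to create a total score of child behaviour problems".
- **Child Report.** The heading is "Child behaviour problems: Child and Adolescent Behaviour Inventory – Child Report". The text beneath repeats the adult entry almost word for word: the same three codes, the same two subscales, a summed total, and the sentence "Parents report on their child’s behaviour during the past month".

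No other place in the protocol gives a CABI code. Section 7 lists child behaviour problems among the outcomes to be reported by both parent and child, in the overall goal, in Objective 1 and in Hypothesis 3.

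**The concern.** The protocol fixes two things here, and each is wrong or contradictory as printed.

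First, three ordered answers carry only two numbers. A rule that sums these codes treats a problem that is very true of the child exactly like one that is only sometimes true, so part of the severity information disappears.

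Second, an outcome labelled as the child's own report is described as a parent's report. Followed to the letter, that sentence would collect the parent's view twice under two outcome names.

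This is not a gap for a statistical analysis plan to fill. The codes and the respondent are stated, and section 26 commits the study to analysing all data according to the registered protocol, so an analysis plan that scored the scale differently would depart from the stated rule. Child behaviour problems belong to Hypothesis 3, and section 20 names child behaviour as a proposed mediator. Section 20 also lists children with existing behaviour problems as a moderator group. Responses are keyed into tablets (section 18). If the printed numbers were programmed as the stored values, the two upper answers could not be separated afterwards.

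**Working it through.** **Inputs (protocol section 15, CABI entries).** Irritability items: 4. Externalising items: 10. Codes: 0, 1, 1. Rule: sum of items.

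**Item count.** 4 + 10 = 14, which reproduces the 14 items stated in the Adult Report entry.

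**Range and change of the total.** Range = 14 × lowest code to 14 × highest code. Change = number of items that move × (new code − old code). The 0/1/2 column is an assumption, because the protocol never states the intended codes.

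| | As printed, 0/1/1 | Assumed, 0/1/2 |
|---|---|---|
| Distinct values per item | 2 | 3 |
| Range of total | 14 × 0 to 14 × 1 = 0 to 14 | 14 × 0 to 14 × 2 = 0 to 28 |
| *Very* to *Somewhat*, all 14 items | 14 × (1 − 1) = 0 | 14 × (1 − 2) = −14 |
| *Very* to *Not True*, all 14 items | 14 × (0 − 1) = −14 | 14 × (0 − 2) = −28 |
| *Very* to *Not True*, 7 items | 7 × (0 − 1) = −7 | 7 × (0 − 2) = −14 |

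Only the move between the two upper answers is invisible. The third row is the most extreme case: a child at the ceiling on every item who stops at the middle answer on every item.

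**Average sensitivity.** All of the following are assumptions: 14 items driven by one latent factor that explains 30% of item variance, a latent improvement of 0.3 SD, 400,000 simulated children per arm, and three mixes of *Not* / *Somewhat* / *Very True* among controls. Standardised effect = (control mean − improved mean) / SD.

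| Answer mix (%) | 0/1/2 | 0/1/1 | Ratio | Correlation of the two scores |
|---|---|---|---|---|
| 60 / 30 / 10 | 0.246 | 0.251 | 0.251/0.246 = 1.02 | 0.97 |
| 40 / 35 / 25 | 0.266 | 0.265 | 0.265/0.266 = 1.00 | 0.96 |
| 25 / 35 / 40 | 0.272 | 0.263 | 0.263/0.272 = 0.97 | 0.94 |

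A repeat of the simulation with the control-arm SD as divisor gave the same pattern to within about 0.007. With the pooled SD the effects were 0.256 v 0.255, 0.269 v 0.261 and 0.271 v 0.253, so the largest loss was 1 − 0.253/0.271 = 7%. The apparent gain in the first mix therefore comes from the choice of divisor. Under either divisor the average loss is small.

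**Was a binary score intended?** Two other entries in section 15 suggest not. For child sexual abuse, where a yes/no variable is wanted, the protocol says that one will be created. For food insecurity, its other item with three ordered answers, it prints 0, 1 and 2.

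**Who reports?** On one side stand the entry's heading (child) and the overall goal, Objective 1 and Hypothesis 3 in section 7 (parent and child). On the other stands one sentence in the body of the entry (parents). The neighbouring child-report entry for prosocial behaviour has an example item addressed to the child in the second person, so the protocol does reword entries for child respondents.

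**The case against.** The strongest reply is that both faults are slips of the pen. Three different labels with a repeated number read as a misprint, and the respondent sentence looks pasted from the adult entry. Similar copying shows elsewhere in section 15: the child-report entry on communication about sexual behaviour speaks of asking caregivers, and some partner-violence entries carry over text about psychological aggression. The field questionnaire may well be right. This is also one secondary outcome among several dozen. All of that stands, and it sets the size of the point. It does not remove the point, because the printed rule is the only one the protocol gives.

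Several stronger readings are tempting, and the protocol does not support them.

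- A reader might infer that improvement from severe to mild problems cannot register at all. Any item that reaches *Not True* still lowers the total, even on the literal coding.
- A reader might infer that the child informant has been dropped. The heading and section 7 still plan a child report; the text contradicts itself on who answers.
- A reader might infer a serious loss of power. The simulation shows little average loss.
- A reader might infer that the moderator grouping is damaged. Section 20 names neither the CABI nor a cut-off for existing behaviour problems, and the simulation did not examine that group, so this remains a possibility only.
- A reader might object that means would not be comparable with other uses of the scale. The protocol reports no such use, so nothing can be said on that.

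**Conclusion.** The point holds as a minor correction. As printed, the CABI total runs 0 to 14 and cannot distinguish the two upper answers in either entry. The respondent in the Child Report entry contradicts that entry's heading and section 7. The expected loss of average sensitivity is small, from none to about 7% of the standardised effect, and that range rests on the assumed answer mixes, factor strength and an even shift across children. That 0/1/2 was meant is an inference from the three labels and from the food insecurity item; the protocol does not say so. What is touched is a Hypothesis 3 outcome, a mediator and possibly a moderator. No primary outcome, primary analysis or power figure depends on it.

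**What to change.** 1. In both CABI entries, print distinct ordered codes for the three answers. The natural reading is 0 = *Not True*, 1 = *Somewhat or Sometimes True*, 2 = *Very True*, with a 14-item total of 0 to 28. The sponsor should confirm this against the questionnaire.
2. Check, before data collection, that the tablets store three different values for the three answers in both the parent and the child questionnaire.
3. In the Child Report entry, replace the sentence naming parents so that children report on their own behaviour, in agreement with the heading and section 7.

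The cost is a text correction in two entries and one check of the tablet coding, with no added burden for participants.

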[Time Frame: Baseline, 8-months post-baseline, and 12-months post-baseline]

Positive partner relationships – Child Report

Positive partner relationships witnessed by children will be based on one item (e.g., “In the past month, how often did your parent figures in your household say nice things to each other in your presence?”). Responses will be based on the past 30 days using a Likert scale ranging from 0=Never to 3=Often. Items will be summed to create a total score of witnessing positive intimate partner relations.

[Time Frame: Baseline, 8-months post-baseline, and 12-months post-baseline]

Positive parenting: Alabama Parenting Questionnaire – Adult Report

Positive parenting will be assessed using 10 items adapted from the Alabama Parenting Questionnaire (APQ-SF)[30]. We will measure frequency of parent involvement (7 items, e.g., “You get involved in activities that your child likes”). Responses will be based on the past 30 days using a Likert scale ranging from 0=Never to 3=Often. Items will be summed to create a total score of positive parenting.

[Time Frame: Baseline, 8-months post-baseline, and 12-months post-baseline]

Positive parenting: Alabama Parenting Questionnaire – Child Report

Positive parenting will be assessed using 20 items adapted from the Alabama Parenting Questionnaire (APQ-SF)[30]. We will measure frequency of parent involvement for both male and female parent figures (14 items, e.g., “Your female/male parent get involved in activities that you like”). Responses will be based on the past 30 days using a Likert scale ranging from 0=Never to 3=Often. Items will be summed to create a total score of positive parenting.

[Time Frame: Baseline, 8-months post-baseline, and 12-months post-baseline]

Parental monitoring: Alabama Parenting Questionnaire – Parent Report

Parental monitoring will be assessed using 6 items adapted from the Alabama Parenting Questionnaire (APQ-SF, e.g., “You tell your child that you like it when they help out in the house or with chores.”)[30]. An additional item has been added to assess monitoring of the use of electronic devices. Responses will be based on the past 30 days using a Likert scale ranging from 0=Never to 3=Often. Items will be summed to create a total score of parental monitoring.

[Time Frame: Baseline, 8-months post-baseline, and 12-months post-baseline]

Parental monitoring: Alabama Parenting Questionnaire – Child Report

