Parenting stress (parent-report) will be based a reduced version of the Parenting Stress Scale (9 items; PSS) [32]. The PSS has been widely used to measure parenting stress, including in LMIC, such as Pakistan [33] and China [34]. The scale has also been used with non-parent caregivers such as grandparents [35]. Caregivers report current and negative attitudes towards their children (e.g., “I feel overwhelmed by the responsibility of being a parent”) related to parenting stress based on a five-point Likert scale (0=Strongly disagree; 4=Strongly agree). Items are summed to create a total parenting stress score.

[Time Frame: Baseline, 8-months post-baseline, and 12-months post-baseline]

Adult depression – Parent Report

Adult depression (parent-report) will be measured using the depression subscale from the Depression, Anxiety, and Stress Scale [36]. Caregivers are asked to respond to items related to how they have felt over the past seven days (e.g., “How often in the past week, have you felt sad or down?”). Responses are coded on a 4-point Likert-like scale, ranging from 0 = Never to 3 = Often. Items are summed with total scores indicating higher levels of adult depression.

[Time Frame: Baseline, 8-months post-baseline, and 12-months post-baseline]

Adult experience of violence during childhood – Parent Report

Adult experience of violence during childhood will be assessed using 6 items covering a range of childhood exposure to violence, including witnessing partner conflict to experiencing corporal punishment and sexual abuse e.g., “How often were you beaten or insulted repeatedly by your parent/family members when you were growing up?”). Responses are coded on a 4-point Likert-like scale, ranging from 0 = Never to 3 = Often. Items will be analysed individually as well as summed to create a total score with higher scores indicating more frequent exposure to violence during childhood.

[Time Frame: Baseline]

Communication about Sexual Behaviour – Parent Report

Communication about sexual behaviour by parents will be assessed by asking caregivers whether or not they have engaged in conversations with their children about puberty and sexual reproductive health (8 items, e.g., “Have you talked to your child about when to have sex?” Items will be summed to indicate number of topics discussed and also analysed qualitatively.

[Time Frame: Baseline, 8-months post-baseline, and 12-months post-baseline]

Communication about Sexual Behaviour – Child Report

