Child report of *communication about sexual behaviour* by parents will be assessed by asking caregivers whether or not their male and female parent figures have engaged in conversations with them about puberty and sexual reproductive health (8 items, e.g., “Has your female/male parent figure ever talked to you about the risks of engaging in sexual acts?”). Items will be summed to indicate number of topics discussed and also analysed qualitatively.

[Time Frame: Baseline, 8-months post-baseline, and 12-months post-baseline]

Impact of COVID-19 – Parent Report

The *impact of COVID-19* will be assessed by asking parents to indicate whether they have been stressed by Covid-19, whether the child has been affected by Covid-19 and where the spouse relationship has been affected by Covid-19 agree.

[Time Frame: Baseline, 8-months post-baseline, and 12-months post-baseline]

Other pre-specified outcomes

Adult experience of violence during childhood – Parent Report

Adult experience of violence during childhood will be assessed using 6 items covering a range of childhood exposure to violence, including witnessing partner conflict to experiencing corporal punishment and sexual abuse e.g., “How often were you beaten or insulted repeatedly by your parent/family members when you were growing up?”. Responses are coded on a 4-point Likert-like scale, ranging from 0 = Never to 3 = Often. Items will be analysed individually as well as summed to create a total score with higher scores indicating more frequent exposure to violence during childhood.

[Time Frame: Baseline]

Basic childhood necessities – Parent Report

Relative poverty will be assessed using an adapted version of the *Basic Necessities Scale* (6 items). Developed by the Centre for South African Social Policy in the ‘Indicators of Poverty and Social Exclusion Project,’ the Basic Necessities Scale measures levels of economic deprivation by identifying basic household items that families are unable to afford [37]. These include food, toiletries, clothes,

shoes, and school uniforms, equipment, and fees. Items are coded dichotomously for positive or negative responses and summed to create an overall score.

[Time Frame: Baseline]

Basic childhood necessities – Child Report

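### Child substance use is defined on lifetime consumption against its own present-tense item, and child-reported sexual-health communication is asked as ever, so follow-up scores can carry pre-baseline events

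*Protocol*

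**What the plan says.** All of this is in the protocol, section 15 (Outcomes measurements), under Secondary outcomes.

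- **Child substance use, child report.** "Child substance use will be measured using two items based on lifetime alcohol and tobacco consumption". The one example item is "Have often do you drink alcohol", answered from 0 (never) to 3 (often). The two items are added: "Items will be summed with higher scores indicating more frequent substance use".
- **Communication about sexual behaviour, child report.** Eight items, for example "Has your female/male parent figure ever talked to you about the risks of engaging in sexual acts". The scoring rule for the eight answers reads as follows: "Items will be summed to indicate number of topics discussed and also analysed qualitatively".
- **Communication about sexual behaviour, parent report.** Eight items, for example "Have you talked to your child about when to have sex". The score is again a count of topics. No recall period is stated.

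All three carry the same schedule: "Time Frame: Baseline, 8-months post-baseline, and 12-months post-baseline".

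Neighbouring scales are bounded in time. Positive parenting and parental monitoring state that "Responses will be based on the past 30 days using a Likert scale ranging from 0=Never to 3=Often". The violence and partner scales use the past month or 30 days, and adult depression uses the past seven days. The measure of adults' own exposure to violence in childhood, which also looks far back, is taken at baseline only.

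Section 20 (Intervention effectiveness) estimates effects on the outcomes after treatment, adjusting for cluster and for the baseline level of the outcome.

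**The concern.** An outcome that is compared between arms after randomisation should be able to move in response to what happens after randomisation. A truthful lifetime or ever answer at 8 or 12 months still contains everything that happened before baseline.

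For substance use, a lifetime total cannot fall. A child who drank before baseline and then stopped would score no lower than one who carried on at a level that leaves the category unchanged. For communication, a topic already discussed before baseline scores one in both arms, whatever happens afterwards. In both cases the difference between arms is pulled towards zero, and a real benefit could be reported as small or absent.

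The substance-use entry has a second problem: the description and the example item do not ask for the same thing. Whoever finalises, translates or reports the questionnaire could follow either one.

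**Working it through.** The protocol gives no effect size, prevalence or power for these outcomes, so there is no figure to reproduce. The check is a reading of the text, followed by arithmetic on assumed rates.

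**Step 1. The text, outcome by outcome**

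| Outcome | Period in the description | Period in the example item | Can pre-baseline events count at follow-up? |
|---|---|---|---|
| Substance use, child | lifetime | present tense, no period | yes under the description; not clearly so under the item |
| Communication, child | none | ever | yes |
| Communication, parent | none | none | open |

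**Step 2. Communication counted as ever**

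Assumptions, none from the documents: each of the 8 topics had already been discussed before baseline with probability b. During follow-up a topic is discussed with probability 0.20 in control and 0.40 in PfR, independently of history.

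- Score counted since baseline: the difference is 8 × (0.40 − 0.20) = 1.60 topics.
- Score counted as ever: the mean is 8 × [b + (1 − b)p], so the difference is 8 × (1 − b) × 0.20 = 1.60 × (1 − b).

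| b | Control | PfR | Difference | Share of 1.60 kept |
|---|---|---|---|---|
| 10% | 2.24 | 3.68 | 1.44 | 90% |
| 50% | 4.80 | 5.60 | 0.80 | 50% |
| 90% | 7.36 | 7.52 | 0.16 | 10% |

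The share lost is b itself, so the size of the problem rests entirely on baseline coverage.

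**Step 3. Substance use, if the lifetime definition is applied**

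This reduces the 0 to 3 score to any use versus none and leaves out baseline adjustment. Assumptions: a share b had used before baseline; 60% of these use again during follow-up in control; new use among never-users is q = 10% to 20% in control; PfR multiplies use during follow-up by 0.70.

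- Use during follow-up: control 0.6b + (1 − b)q, PfR 0.70 times that. The risk ratio is 0.70 by construction.
- Lifetime use: control b + (1 − b)q, PfR b + (1 − b) × 0.70q.

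| b | q | Lifetime, control | Lifetime, PfR | Risk ratio |
|---|---|---|---|---|
| 5% | 10% | 14.5% | 11.65% | 0.80 |
| 5% | 20% | 24.0% | 18.3% | 0.76 |
| 20% | 10% | 28.0% | 25.6% | 0.91 |
| 20% | 20% | 36.0% | 31.2% | 0.87 |
| 40% | 10% | 46.0% | 44.2% | 0.96 |
| 40% | 20% | 52.0% | 48.4% | 0.93 |

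The whole visible effect comes from never-users. The effect among earlier users drops out.

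**Step 4. Does baseline adjustment repair this?**

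No. Conditioning on the baseline score removes variance carried forward from before baseline and so helps precision. It does not create information about reduced use among earlier users, or about renewed talk on a topic already covered, because the follow-up answer does not record either.

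**The case against.** The case on the other side has several parts, and much of it stands.

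- **The item shown is not a lifetime item.** A present-tense frequency question can go down when a child drinks less. A reader might infer from the description that substance use is in fact asked over the lifetime. The protocol does not establish that; it shows a contradiction. This limits the point to a conflict to be resolved, with a loss only if the description prevails.
- **Even a lifetime score on 0 to 3 is not a yes/no score.** Prevented escalation would register as well as prevented initiation, so it would be wrong to say that only new users can show an effect.
- **The parent communication item does not say ever.** Lifetime is a natural reading but it is not written.
- **A count of topics ever covered is a coherent outcome.** Newly raised topics increase it, and randomisation keeps the comparison fair. This stands, but the protocol nowhere says that cumulative coverage is intended.
- **The size is unknown.** A reader might infer that most of the effect is lost or hidden. With low baseline coverage, which is plausible for some topics, most of the contrast remains.
- **Open recall periods are not peculiar to these outcomes.** Education support, prosocial behaviour and respectability state none either. True, but those entries do not define the score on lifetime events or word the item as ever.

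The point cannot be left to a statistical analysis plan. The recall period is set in the questionnaire, and once the answers are in, no analysis can separate events before baseline from those after.

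**Conclusion.** The point holds in limited form. The substance-use entry contradicts itself. If its lifetime definition is applied, the follow-up score cannot register stopping or cutting down, and earlier use dilutes the arm contrast: under the stated assumptions a risk ratio of 0.70 would appear as 0.76 to 0.96, for baseline use between 5% and 40%. The child-report communication item counts pre-baseline topics at 8 and 12 months and keeps a share of about 1 − b of the difference, that is 90%, 50% or 10% at assumed coverage of 10%, 50% or 90%. The parent-report item has no stated period, so for it the matter is open.

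The rates are assumptions, and the communication result also assumes that new talk is independent of earlier coverage. The documents supply neither baseline use nor baseline coverage, so no single loss figure should be quoted. Effects would be diluted, not necessarily hidden: new initiation, escalation and newly raised topics still show. Only secondary outcomes are concerned; the primary outcomes and the power statement in section 13 are untouched.

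**What to change.** **Substance use.** Delete the word lifetime from the description and ask both items over the past 30 days at all three visits, as in the neighbouring scales. The never-to-often responses can stay. The cost is a change of stem in two child items. A 30-day period will also catch fewer users than a longer one, to an extent the documents do not let one judge.

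**Communication, child and parent report.** Choose one of two routes and write it into section 15.

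1. State that the outcome is cumulative topic coverage, adjusted for baseline, and give the parent item the same explicit period as the child item. This leaves the child item as it is and accepts the dilution in the open.
2. At both the 8- and 12-month visits, ask about the time since the baseline interview, and use the baseline score only as a covariate. This changes the stem of 8 child and 8 parent items and adds none. The downside is that baseline and follow-up scores then cover different periods and cannot form a change score.

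Asking about the time since the last interview would be a poor substitute. It covers about 8 months at the first follow-up and 12 − 8 = 4 months at the second. At 12 months it would also drop topics raised before the 8-month visit. The 16 weekly sessions (section 14) and the 8-month timing of the process measures suggest that this is when the programme is delivered.

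The changes are nearly free if made before the questionnaires are translated. If data collection has begun, the wording actually used should be documented and the outcome described to match it.
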